#### **Patients with Pre-Diabetes (At risk):**

- Ages 18 and older
- BMI  $\geq 25 \text{ kg/m}^2$
- patients who have either: (1) had at least 2 outpatient primary care visits in one of the PaTH health systems in the past 3 years (since January 1, 2012), or (2) for whom claims data are available

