### **3.2 Exclusion Criteria**

- Patients under the age of 18

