### 4.2 Identification of subjects/charts/existing data

The University of Pittsburgh is the lead site for the PaTH Network. The overall operations of the PaTH Network are run by the PaTH Steering Committee, which will leverage the data infrastructure, established governance and regulatory policies related to data security, data sharing and human subjects protection of the PaTH Network.

We will use the PaTH Network to identify potential patients who meet our eligibility criteria. PaTH's infrastructure enables and allows for the development, validation, and deployment of electronic algorithms for identifying patients with the conditions of interest. PaTH will continue to follow the guidance of the NIH Health Systems Collaboratory's work on EHR-based phenotyping to create computable phenotypes for the proposed diabetes and pre-diabetes cohorts. Phenotypes will be based on the above inclusion/exclusion criteria.

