### 7.2 Study Procedures

For the specific needs of this proposal, we will define 2 patient cohorts using the PaTH Network: (1) Diabetes cohort and (2) At-risk for diabetes cohort. As demonstrated in the table below, there are over 328,000 patients with a diagnosis of diabetes (defined as age 18 and older with a diagnosis of diabetes mellitus – ICD9 250.xx) and over 2 million patients at risk for diabetes (defined as age 18 and older with a BMI of  $\geq 25$ ) within the PaTH network.

Patient Characteristics	Penn State University (N=25,219)	University of Pittsburgh (N=150,589)	Johns Hopkins University (N=60,324)	Temple University (N=40,536)	University of Utah (N=51,787)	PaTH Total (N=328,455)
Patients with Diabetes						
Insurance type						
Private	9,874 (38%)	60,223 (40%)	32,371 (54%)	5,261 (13%)	21,264 (41%)	128,993 (39%)
Medicaid	1,890 (8%)	10,165 (7%)	727 (1%)	21,759 (54%)	4,189 (8%)	38,730 (12%)
Medicare	12,998 (52%)	54,675 (36%)	22,826 (38%)	10,916 (27%)	23,997 (46%)	125,412 (38%)
Uninsured	457 (2%)	11,625 (8%)	485 (1%)	2,599 (6%)	2,337 (5%)	17,503 (5%)
Race						
White	21,780 (86%)	116,056 (77%)	32,544 (54%)	14,347 (35%)	39,580 (76%)	224,307 (68%)
African-American	1,679 (7%)	15,336 (10%)	20,053 (33%)	14,656 (36%)	944 (2%)	52,668 (16%)
Other	1,760 (7%)	19,197 (13%)	7,727 (13%)	11,533 (29%)	11,263 (22%)	51,480 (16%)
Hispanic Ethnicity	1,054 (4%)	697 (0.5%)	2,002 (3%)	7,356 (18%)	6,077 (12%)	17,186 (5%)
Female Gender	12,014 (48%)	70,623 (47%)	30,912 (51%)	22,485 (55%)	25,727 (50%)	161,761 (49%)
Patients At-Risk for Diabetes						
	(N=167,799)	(N=950,020)	(N=471,860)	(N=212,314)	(N=260,506)	(N=2,062,499)
BMI						
25-29.9	69,353 (30%)	433,799 (31%)	226,113 (32%)	92,807 (31%)	122,583 (31%)	944,655 (32%)
30-34.9	48,353 (21%)	268,236 (19%)	128,799 (18%)	60,330 (20%)	87,023 (22%)	592,741 (20%)
35-39.9	25,388 (11%)	128,113 (9%)	58,072 (8%)	29,930 (10%)	70,774 (18%)	312,277 (10%)
40+	24,705 (11%)	94,550 (7%)	43,377 (6%)	23,321 (8%)	25,410 (7%)	211,363 (7%)

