***Diabetes Cohort Definition.*** During year 1 of the proposed project, the investigative team, in collaboration with the PaTH Network, will identify a valid cohort of patients with type 2 diabetes. The cohort of patients under study will be defined as all patients age 18 and older with an indication of type 2 diabetes during the proposed study time frame. Patients will be classified as having diabetes using a clinically validated algorithm: type 2 diabetes mellitus on the problem list, diabetes-specific medications, hemoglobin A1c (HbA1c) results > 7.0%, or one inpatient diagnosis code or two outpatient diagnosis codes for type 2 diabetes (ICD-9 codes 250.xx). The diabetes cohort will be further limited to patients who will likely be captured in the PaTH EHR records or claims data so that outcome assessments can occur. Thus, we will further limit the diabetes cohort to patients who have either: (1) had at least 2 outpatient primary care visits in one of the PaTH health systems in the past 3 years (since January 1, 2012), or (2) for whom claims data are available. The cohort will be dynamic, with new patients added into the cohort after 2015 as they meet the diabetes cohort definition prospectively. The observational period for the outcome variables will be for the 10-year period from 2009-2019, thus including 3 years of data prior to the first policy change (CMS instituting coverage for intensive behavioral therapy for obesity) and 3 years after the last policy change (Pennsylvania Medicaid expansion) under study.

Following the definition of the diabetes cohort and key diabetes outcomes and covariates as described above, an initial extraction of variables will be conducted in Year 2 of the proposed project for years 2009-2015. This early data extraction from the PaTH Network will allow for cohort validation and data cleaning and editing, as well as required programming and determination of the analysis models. We will utilize this initial data extraction in Years 2 and 3 to analyze the impact of early health policy changes, as well as to prepare a manuscript of both the protocol and early findings of policy impact. The final data extraction will occur during the final quarter of Year 4 of the proposed project, allowing for completion of a ten-year time period (2019).

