***At-risk Cohort Definition.*** The cohort of patients under study will be defined as patients age 18 and older who are at risk for the development of diabetes, based on being overweight. Patients seen at one of the four PaTH institutions will be included in the at-risk cohort if they have a  $BMI \geq 25 \text{ kg/m}^2$ , based on most recent recorded weight and at least one recorded height. The at-risk cohort will be further limited to patients who will likely to be captured in the PaTH EHR records or claims data so that outcome assessments can occur. Thus, we will further limit the at-risk cohort to patients who have either: (1) had at least 2 outpatient primary care visits in one of the PaTH health systems in the past 3 years (since January 1, 2012), or (2) for whom claims data is available. The cohort will be dynamic, with new patients added into the cohort after 2015 as they meet the at-risk cohort definition prospectively. Patients will not be removed from the cohort, even if they are no longer overweight. The observational period for the outcome variables will be for the 10-year period from 2009-2019, thus including 3 years of data prior to the first policy change (CMS instituting coverage for intensive behavioral therapy for obesity) and 3 years after the last policy change (Pennsylvania Medicaid expansion) under study.

[figure not shown]
intensive behavioral therapy for obesity) and 3 years after the last policy change (Pennsylvania Medicaid expansion) under study.

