**Table 1. Proposed Outcomes for the Pre-diabetes and Diabetes Cohorts**

Outcomes	Definition	Notes
Pre-diabetes cohort		
Weight loss during counseling	Weight lost from first IBT visit to final IBT visit	Available at all PaTH sites
Weight loss maintenance	% of weight lost during program and maintained over remaining time period, reported by year	Available at all PaTH sites
Diabetes incidence	% of patients who develop diabetes per year following weight counseling	Available at all PaTH sites
Patient-reported outcomes	-SF-12 -PHQ-2, PHQ-8, PHQ-9 -Physical function -sleep -fruit and vegetable consumption -social support -physical activity -PROMIS (PROMIS 29, physical function, depression) -healthy lifestyles -patient reported medication reconciliation	Available at some sites – Formal inventory of PROs will be collected at each institution at the beginning of the project, to be included as secondary outcomes
Diabetes cohort		
Weight loss during counseling	Weight lost from first IBT visit to final IBT visit	Available at all PaTH sites
Weight loss maintenance	% of weight lost during program and maintained over remaining time period, reported by year	Available at all PaTH sites
Patient reported outcomes	-SF-12 -PHQ-2, PHQ-8, PHQ-9 -Physical function -sleep -fruit and vegetable consumption -social support -physical activity -PROMIS (PROMIS 29, physical function, depression) -healthy lifestyles -patient reported medication reconciliation	Available at some sites – Formal inventory of PROs will be collected at each institution at the beginning of the project, to be included as secondary outcomes
Uncontrolled diabetes	Average A1c > 9 or no A1c	Available at all PaTH sites
Controlled blood pressure	SBP < 140, DBP < 90, averaged across values over year	Available at all PaTH sites
On a statin medication	Evidence of a statin medication on current EHR medication list	Available at all PaTH sites
Receiving annual eye exam	Documentation of eye exam once in past year	Available at all PaTH sites
Receiving annual urinary microalbumin test	Documentation of lab testing for urinary microalbumin at least once in past year	Available at all PaTH sites
Lower extremity amputations	Documentation of procedure for lower extremity amputation or billing code through health plans in past year	Available at all PaTH sites

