Furthermore, we will use the similar models as described above to evaluate post-policy impact of obesity screening and counseling (number of visits) on the outcomes such as weight loss, diabetes incidence, and diabetes outcomes (including hemoglobin A1c, controlled blood pressure, use of a statin medication). The outcome data collected after the universal coverage change (i.e.,  $t = 0, 1, \dots, 6$ ) will be used to estimate the trend of change. The number of screening and counseling will be used as a predictor in the mixed effects models. The effects of patient and practice characteristics will also be examined in the models. Statistical software SAS 9.4 and R environment will be used to implement the proposed analyses.

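### The at-risk cohort criteria do not exclude existing type 2 diabetes, although diabetes incidence is an outcome of that cohort

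*Combined protocol and SAP*

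**What the plan says.** **At-risk cohort.** Sections 3.1 and 7.2 (At-risk Cohort Definition) ask for adult age, a BMI of 25 kg/m² or more, and either two primary care visits since January 1, 2012 or available claims data. Section 7.2 puts it as "Patients seen at one of the four PaTH institutions will be included in the at-risk cohort if they have a" BMI at or above that value. The whole of Section 3.2 is one exclusion: "Patients under the age of 18". Section 4.2 then says how the cohorts will be programmed: "Phenotypes will be based on the above inclusion/exclusion criteria". The count in Section 7.2 follows the same logic, with "over 2 million patients at risk for diabetes (defined as age 18 and older with a BMI of" 25 or more.

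**Diabetes cohort.** Section 7.2 takes "all patients age 18 and older with an indication of type 2 diabetes during the proposed study time frame". Evidence may come from the problem list, medication, HbA1c or coded diagnoses. There is no BMI limit.

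**Outcome.** Table 1 lists diabetes incidence for the pre-diabetes cohort, as the percentage "of patients who develop diabetes per year following weight counseling". Aims 1 and 2 in Section 1.0 both name it. Section 8.0 uses post-coverage data to "evaluate post-policy impact of obesity screening and counseling (number of visits) on the outcomes such as weight loss, diabetes incidence, and diabetes outcomes".

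**Leaving the cohort.** The only statement in Section 7.2 about removal is that patients stay in the at-risk cohort if they stop being overweight. Nothing is said about patients who have, or acquire, diabetes.

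**The concern.** An incidence needs a population free of the disease at the start and a rule for who is still at risk in each later year. The listed criteria supply neither. A patient with long-standing type 2 diabetes and a BMI of 25 or more satisfies both cohort definitions, and nothing gives one cohort precedence.

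Such a patient cannot develop diabetes again, so leaving the patient in the denominator lowers the annual percentage. For Aim 2, which compares patients who receive counseling with those who do not, the dilution cancels only if existing diabetes is equally common in both groups. If it is not, the comparison shifts even when counseling has no effect on incidence. The very large sample described under Statistical Power in Section 8.0 does nothing to reduce a bias of this kind.

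A smaller, related gap concerns BMI. Section 1.0 ties the counseling visits to obesity, while the cohort starts at a BMI of 25, so receipt may vary with BMI. BMI is not named among the exposure variables in Table 1 or the propensity score inputs in Section 8.0.

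**Working it through.** **1. Can one patient meet both definitions?** Take an adult with type 2 diabetes on the problem list, a BMI of at least 25 and two qualifying visits.
- Section 3.1, diabetes list: met.
- Section 3.1, at-risk list: met on age, BMI and visits.
- Section 3.2: not excluded.
- Section 4.2: the phenotypes come from these lists, so both would select the patient.

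**2. The plan's own totals** (Section 7.2 table, five sites).
- Diabetes: 25,219 + 150,589 + 60,324 + 40,536 + 51,787 = 328,455, as printed.
- At risk: 167,799 + 950,020 + 471,860 + 212,314 + 260,506 = 2,062,499, as printed.

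**3. Limit on the overlap in the tabulated counts.** Let f be the share of the diabetes count that also has a BMI of 25 or more. The documents do not give f, so it is an assumption ranged over its possible values. The overlap share is s = f × 328,455 / 2,062,499. If existing cases stay in the denominator and are never counted as events, observed incidence = (1 − s) × true incidence. The last column assumes a true incidence of 1% per year. Counts are rounded separately.

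| f (assumed) | Overlap | s | At-risk count without overlap | Observed incidence |
|---|---|---|---|---|
| 0 | 0 | 0% | 2,062,499 | 1.00% |
| 0.50 | 164,228 | 8.0% | 1,898,272 | 0.92% |
| 0.75 | 246,341 | 11.9% | 1,816,158 | 0.88% |
| 0.90 | 295,610 | 14.3% | 1,766,890 | 0.86% |
| 1 | 328,455 | 15.9% | 1,734,044 | 0.84% |

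The relative understatement equals s whatever the true incidence. The 15.9% limit belongs to this table only. The 328,455 counts ICD-9 250.xx diagnoses, whereas the Section 3.1 algorithm also admits problem-list, medication and HbA1c evidence. The visit or claims condition would change both counts.

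**4. Effect on the Aim 2 comparison.** With no true effect, the rate ratio of receivers to non-receivers is (1 − s_R) / (1 − s_N), and the true incidence cancels. The documents give neither share. For assumed shares of 15% in receivers and 5% in non-receivers, it is 0.85 / 0.95 = 0.89, a spurious benefit. With the shares reversed, it is 0.95 / 0.85 = 1.12. With equal shares it is 1.

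**5. The other reading, for illustration only.** If existing cases were counted as new when first recorded, first-year incidence would be s + (1 − s) × true incidence. For an assumed s of 1%, a true 0.5% becomes 0.01 + 0.99 × 0.005 = 1.50% (3.0 times), and a true 2% becomes 0.01 + 0.99 × 0.02 = 2.98% (1.5 times).

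**The case against.** The best defense is that the intent is plain. Section 3.1 opens the list with "Patients with Pre-Diabetes (At risk", Section 7.2 speaks of patients who may go on to acquire diabetes, Table 1 separates two cohorts, and its outcome is worded in terms of developing the disease. Sections 4.2 and 7.2 also foresee phenotype and cohort validation. This stands as evidence of intent, and it rules out the inference that the sponsor chose to include existing cases. It does not supply an operational rule. Section 4.2 builds the phenotypes from criteria that contain no diabetes test, and intent does not fix the date at which diabetes status is judged or when a patient leaves the risk set.

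A reader might infer that existing cases will be counted as new disease and incidence inflated several-fold. The documents do not support that: "of patients who develop diabetes per year following weight counseling" does not fit a patient whose diabetes was recognized before counseling. A reader might also take any patient who appears in both cohorts as an error. Later entry into the diabetes cohort is expected, because Section 7.2 adds patients prospectively as they qualify.

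On BMI, the lists are open-ended, so this is a gap in prespecification and not a contradiction. Nor does the plan propose to adjust for BMI measured after counseling. It describes BMI from the most recent weight for eligibility only.

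**Conclusion.** The point holds. As written, the criteria leave existing type 2 diabetes in the denominator of an incidence outcome, and no rule assigns patients who meet both definitions. The effect is to understate incidence by the overlap share and to bias the Aim 2 comparison if that share differs between the groups.

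The size is not known. On the tabulated counts the understatement is at most 15.9% in relative terms, and that limit should not be read as an estimate or as a limit for the cohort that the full algorithm will produce. The rate ratios of 0.89 and 1.12 rest on assumed shares of 15% and 5% and show only that either direction is possible. The counted-as-new figures depend on a reading that Table 1 resists and should carry no weight in judging severity. The absence of BMI from the named Aim 2 covariates is a secondary matter.

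**What to change.** For the incidence analysis, add these rules to Section 7.2 and Section 8.0:

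- **Entry date.** At-risk entry is the first date in the study period on which the BMI and visit or claims criteria are met. For Aim 2 it is no earlier than the start of the post-coverage window in Section 8.0, whose calendar date should be stated.
- **Exclusion at entry.** Patients who meet the Section 3.1 diabetes algorithm on or before that date are excluded and analyzed in the diabetes cohort. The rule must be dated. Excluding everyone who ever meets the algorithm would remove the incident cases themselves.
- **Risk set.** Each later year counts only patients still diabetes-free at its start.
- **Sensitivity analysis.** Repeat with a minimum look-back before entry, since an existing case first recorded after entry would otherwise pass as incident.
- **BMI (secondary).** In the Aim 2 model and the propensity score, include the last BMI recorded on or before the same entry date, by the same rule for receivers and non-receivers.

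The visit rule counts from January 1, 2012, so patients who qualify only through visits cannot enter in 2009 to 2011 as it stands. The sponsor should say how those years are handled for Aim 1 incidence.

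The cost is an entry date and a dated diabetes flag, the latter from an algorithm the plan already runs, and an incidence cohort smaller by an unknown share. The look-back will shrink it further in the sensitivity analysis. Some patients will have no weight before entry, so a missing-data rule is needed, and some may have been counseled before entry, which the BMI covariate cannot undo.

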## 1.0 Objectives

The overarching goal of this proposal is to understand the comparative effectiveness of obesity counseling as covered by Centers for Medicare and Medicaid Services (CMS) in improving weight loss for adults either with or at high risk of type 2 diabetes. CMS and most insurers now include obesity screening and counseling benefits, with no cost sharing to patients. Since overweight patients are at highest risk for diabetes, improved weight management services could prevent diabetes and its negative health outcomes. Beneficiaries with obesity are eligible for up to 20 face-to-face visits for weight counseling in the primary care setting. We propose comparing weight and diabetes outcomes in three states using electronic health record (HER) and claims data before and after this policy was implemented. The PaTH network brings together six academic health systems – the University of Pittsburgh/University of Pittsburgh Medical Center, Penn State College of Medicine/Hershey Medical Center, Temple University School of Medicine/Temple Health, and the Johns Hopkins University/Johns Hopkins Health System/Johns Hopkins Health Care, Geisinger Health Systems, and The University of Utah – to function as an integrated research network and learning health system, providing an infrastructure for observational studies, such as the one proposed here, that require populations beyond a single health system to answer important patient-centered health services questions ([www.pathnetwork.org](http://www.pathnetwork.org)). Using the PaTH Clinical Data Research Network (CDRN) infrastructure, we propose the following specific aims:

**Aim 1: Evaluate the impact of universal preventive service coverage for obesity screening and counseling on weight loss, diabetes incidence, and diabetes outcomes, in patients with diabetes or at high risk for diabetes (defined by body mass index (BMI)  $\geq 25$ ).** We will determine how the annual probability of receiving obesity and/or nutritional counseling (as defined by Current Procedural Terminology (CPT) code) changed pre- and post-policy across all insurers in a cohort of patients with diabetes and at high risk for diabetes. We hypothesize that individual patients are more likely to receive counseling following coverage implementation. Further, we hypothesize that patients who receive a greater number of face-to-face visits will have greater weight loss compared to those who receive fewer visits.

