## 2.0 Background

### 2.1 Scientific Background and Gaps

Overweight and obesity are America's number one health concern. The prevalence of obesity in the US is greater than 36%, which is far above the Healthy People 2020 objective of less than 30.5%. Perhaps most concerning is the rate that obesity has increased, having doubled since 1970. As the second most preventable cause of death, obesity is a risk factor for diabetes, cardiovascular disease, stroke, and cancer, all major causes of death in the US. Addressing obesity through lifestyle interventions decreases the risk of developing type 2 diabetes, a disease which affects over 29 million people (9.3% of the US population). Diabetes is associated with serious complications, including cardiovascular disease, blindness, renal failure and lower extremity amputation. Although complications are preventable with proper medical and lifestyle management, including weight loss, nearly half of patients with diabetes do not have adequate glycemic control.

Primary care clinics may be an ideal setting for weight control interventions. Greater than 80% of Americans see a PCP regularly and access to primary care is expected to increase with health care reform. Further, as PCPs identify and treat the multitude of conditions affected by being overweight, including diabetes, they are ideally positioned to best engage their patients in weight management. The Centers for Medicare and Medicaid Services (CMS) implemented a healthcare procedure coding system code for intensive behavioral therapy (IBT) for obesity within primary care settings in 2012 to facilitate payment for addressing obesity, which was followed by universal coverage by insurers for IBT for adults of all ages in 2013. However, the impact of this coverage on patient-centered outcomes is largely unknown.

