In the multi-level modeling, the first-level unit is the yearly measurement for the individual subject (pre- and post-policy), the second-level unit is the individual subject, the third-level unit is the health system or clinic within the health system (cluster), and the fourth-level unit is the state. We set year 2014 as time origin for Utah when considering the policy impact of the ACA. Let  $Y_{ijkt}$  denote the binary response of having controlled diabetes at year  $t$  since policy changes for the  $k^{\text{th}}$  subject within the  $j^{\text{th}}$  cluster of the  $i^{\text{th}}$  state,  $t = -5, -4, \dots, 0, 1, \dots, 5$ ,  $i = 1, 2, 3$ ;  $j = 1, 2, \dots, c_i$ , and  $k = 1, 2, \dots, n_{ij}$ , where  $c_i$  is the number of clusters within the  $i^{\text{th}}$  state and  $n_{ij}$  is the sample size within the  $j^{\text{th}}$  cluster of the  $i^{\text{th}}$  state. An individual subject may not be in the system for all 11 timepoints of measurement, so  $t$  will have a smaller range of values for that individual subject. Also due to the different timeline of policy changes, the number of years before and after policy changes may vary. The probability of having controlled diabetes,  $\mu_{ijkt} = E(Y_{ijkt}) = \Pr[Y_{ijkt} = 1]$ , can be described by the following segmented logistic regression model

$$\begin{aligned} \text{logit } \mu_{ijkt} &= \log \{\Pr[Y_{ijkt} = 1] / \Pr[Y_{ijkt} = 0]\} \\ &= \beta_{0ijk} + (t + 5) \beta_{1ijk} && \text{if } -5 \leq t \leq 0, \text{ pre-period before policy changes} \\ &= \beta_{0ijk} + 5 \beta_{1ijk} + t \beta_{2ijk} && \text{if } 0 \leq t \leq 5, \text{ post-period after policy changes} \end{aligned}$$

where  $\beta_{mijk}$  ( $m = 0, 1, 2$ ) are subject-specific regression parameters, with  $\beta_{0ijk}$  being the log odds of having controlled diabetes at  $t = -5$ , and  $\beta_{1ijk}$  and  $\beta_{2ijk}$  being the slopes (annual change in log odds) for the pre- and post-periods, respectively. In the framework of a mixed-effects model, each  $\beta_{mijk}$  is modeled by

$$\beta_{mijk} = \mathbf{x}_{mijk}^T \boldsymbol{\beta}_m + \mathbf{z}_{ij}^T \boldsymbol{\gamma}_{1ij} + \boldsymbol{\gamma}_{2mijk}$$

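### EHR patients are selected on primary care visits in 2012-2014 with no matching rule for 2009-2011, so counseling and visit rates shift around the policy dates with no policy effect

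*Combined protocol and SAP*

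**What the plan says.** Section 7.2 defines the diabetes and at-risk cohorts, and Section 3.1 repeats the criteria. A patient enters by one of two routes: the patient has "had at least 2 outpatient primary care visits in one of the PaTH health systems in the past 3 years (since January 1, 2012", or is someone "or (2) for whom claims data is available". The stated purpose is to keep "patients who will likely to be captured in the PaTH EHR records or claims data so that outcome assessments can occur".

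Section 2.1 says that CMS introduced a "code for intensive behavioral therapy (IBT) for obesity within primary care settings in 2012", "which was followed by universal coverage by insurers for IBT for adults of all ages in 2013". Section 7.2 observes outcomes from 2009 to 2019 and counts three years before the first policy change. New patients join both cohorts after 2015. A first extraction covering 2009-2015 is to be analyzed and written up in Years 2 and 3.

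Aim 1 (Section 1.0) asks "how the annual probability of receiving obesity and/or nutritional counseling" changed from before to after the policy. Section 8.0 reads the policy effect from the change in slope between two segments. It allows that "An individual subject may not be in the system for all 11 timepoints of measurement", but does not define being in the system or say how a year without contact is scored.

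**The concern.** The visit window opens in the year CMS coverage began, one year before universal coverage. Every EHR-route patient in the initial cohort therefore has at least two visits somewhere in 2012-2014. The same patient may have none in 2009-2011.

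Counseling, clinic visits, eye exams and microalbumin tests can be recorded only if the patient has contact with care. Table 1 also scores a year with no A1c as uncontrolled diabetes, so for that outcome a year without contact is counted rather than dropped. Selection on later contact can thus produce a pre/post difference in these outcomes on its own.

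Nothing else in Section 8.0 corrects it. The offset in the count model is unspecified, and neither the propensity-score nor the subgroup section deals with selection on visits after January 2012. Section 8.0 also stresses that very small effects will be detectable, so an artefact of a few percent would probably reach significance.

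A second issue is that IBT is delivered in primary care and IBT visits are not excluded from the entry count. A patient can therefore qualify through the exposure itself, which bears on Aim 2.

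**Working it through.** **Dates.** 2012 - 2009 = 3 pre-policy years (2009, 2010, 2011), which agrees with Section 7.2. Three years from January 1, 2012 gives an entry window of 2012-2014.

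**Exact case, no turnover, no policy effect.** The inputs are assumptions, since the documents give no visit or counseling rates: each patient has a constant visit rate, gamma-distributed with mean 1 per year and shape 1, and each visit carries a 5% chance of counseling. Let N be the visits in the three-year window.

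- P(N = n) = (1/4)(3/4)^n, so E[N | N ≥ 2] = 2 + 3 = 5. Visits per year inside the window: 5/3 = 1.67.
- Outside the window, the expected rate given N = n is (n + 1)/4, so the mean is (5 + 1)/4 = 1.50 per year.
- Ratio: 1.67/1.50 = 1.11.
- Counseling outside the window: with a = 4/4.05, 1 - a³(0.25)/(1 - 0.75a) = 7.1% per year.
- Counseling inside the window: with b = 1 - 0.05/3, 1 - b²(0.25)/(1 - 0.75b) = 7.9% per year.

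**Simulation, no policy effect.** 400,000 patients per scenario, 5% counseling per visit, 70% in the system at any time where there is turnover, all years counted:

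| Mean visits/yr, annual exit | Counseling 2009-11 → 2012-14 | Ratio | Slope change, origin 2012 / 2014, data to 2019 | Same, data to 2015 |
|---|---|---|---|---|
| 1, 15% | 5.54% → 7.25% | 1.31 | -0.181 / -0.134 | -0.175 / -0.376 |
| 2, 10% | 8.36% → 9.88% | 1.18 | -0.133 / -0.101 | -0.116 / -0.225 |
| 3, 0% | 14.42% → 14.66% | 1.02 | -0.010 / -0.007 | -0.012 / -0.027 |

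Slope changes are in log-odds per year. Further runs at 3% counseling per visit, with means of 2.5, 1.5 and 1 visits per year, gave ratios of 1.16, 1.21 and 1.29 with 10% turnover, and 1.03, 1.07 and 1.11 without.

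**Why the slope change is negative.** In Section 8.0 the pre-segment is β0 + (t + 5)β1 and the post-segment is β0 + 5β1 + tβ2. Both equal β0 + 5β1 at t = 0, so the model has no level-change term. The artefact is a bump. In the second scenario, visits per year run 1.74, 1.80, 1.88 (2009-2011), then 2.13, 2.13, 2.12 (2012-2014), then 1.89 in 2015, falling to 1.67 by 2019. A continuous two-piece line fits this with a false positive pre-slope and a lower post-slope.

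**Sensitivity to how years are counted.** With 10% turnover:

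- Counting only years in the system gave ratios of 1.01, 1.08 and 1.16 (means 2.5, 1.5, 1.0). A separate set gave 1.03 to 1.10.
- Counting only years with a visit gave 0.97 to 1.00.
- Counting from first recorded contact gave 0.89 to 0.93, partly because records start in 2009.

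Across the 5% scenarios, adding later entrants with all their back years cut the rise to 0-8%.

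**Check of a uniform rule.** Counting a person-year only after at least two visits in the preceding three years gave ratios of 1.00 for visits and counseling, with slope changes within 0.002 of zero.

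**The case against.** A reader might infer that the rule guarantees contact in every early covered year and so inflates the Aim 1 result by a quarter or so in favor of the hypothesis. The documents do not support that, for four reasons.

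- **Guarantee.** It is two visits somewhere in 2012-2014. Both may fall in 2014.
- **Direction.** Section 8.0 measures policy impact by slope change, and the artefact pushes that parameter against the hypothesis. Only the looser before/after wording of Aim 1 is biased in favor.
- **Size.** The larger ratios need turnover and need years outside the system to be scored as no counseling. Section 8.0 says such patients contribute a shorter range of years, which may mean those years are dropped. The rise then shrinks, and under some readings it vanishes or reverses.
- **Dilution and timing.** Claims-route patients face no visit rule, and their share is not given. Entrants after 2015 dilute the effect further. Universal coverage is dated 2013, so for that policy the window opens a year early.

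All four stand as limits on size and direction. They do not remove the asymmetry, because the plan never says which years count. Dilution by later entrants also gives little help to the 2009-2015 analysis, since those entrants join after 2015.

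**Conclusion.** The entry rule treats the pre- and post-policy years differently and shifts contact-dependent outcomes without any policy effect. For annual counseling, 2012-2014 against 2009-2011, the false rise is about 2-11% with no turnover or when only in-system years count (single runs gave 1% and 16%). It is about 15-30% with 10% annual turnover and all years counted. Both ranges come before dilution and rest on assumed visit rates, turnover and counseling rates.

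The bias runs toward a policy effect in a raw period comparison and toward a false negative slope change in the planned model. One rule distorting two readings in opposite directions makes either hard to interpret. The size of the effect from IBT visits counting toward entry is unknown. This should be settled before the 2009-2015 data are analyzed.

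**What to change.** Replace the fixed window in Sections 3.1 and 7.2 with one contact rule applied identically to each calendar year 2009-2019. For example, a person-year counts if the patient had at least two primary care visits in the preceding three years, not counting obesity or nutritional counseling visits, or is enrolled in claims that year. Use this rule to define being in the system in Section 8.0, do not keep the 2012-2014 filter on top of it, and report results by entry route.

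The rule needs visit records from 2006 for the 2009 person-year (2009 - 3 = 2006). If data before 2009 are not extracted, require at least two such visits in both 2009-2011 and 2012-2014. That balances the two period means. It conditions on nothing after 2014, so it does not by itself protect the slope-change estimate.

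Do not make a non-counseling visit in the same year the primary rule. It would drop years whose only primary care contact was counseling, which coverage may itself create, and so could remove genuine uptake.

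The cost is protocol wording and extraction code, plus the earlier visit records if the preceding-three-years rule is used. Some person-years are lost, and the estimate then applies to patients established in care.
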